2.7.3.2 Patient perception of antidepressant effectiveness and side effects

Patients' self-reported clinical differences (release patterns, antidepressant effectiveness, and adverse events) will be compared between all bupropion 300mg XL products (brand vs. generics, and between generics).

Reports will be determined by the daily patient smart phone assessments. Daily depressive symptom scores, side effect scores, and focus group-nominated symptoms (e.g., sensations regarding drug release) during each randomized bupropion phase will be compared with each other, and with those from the open-label lead-in period. Repeated measures ANOVA analogues of the models described above for the pharmacokinetic parameters will be used for assessing patents' perceptions. Since there are no well-accepted criteria for the equivalence of scores using this method, any systematic effects of differences between patient's responses to Wellbutrin XL and each generic product will be tested.

Analysis will explore whether differences in smart phone-collected depression symptoms, side effects, and patient reports regarding release patterns are related to pharmacokinetics by augmenting the models above with pharmacokinetic parameters as covariates. Analysis will determine if there are differences in bupropion products by correlating, on an individual basis, the ratio of the two pharmacokinetic parameters to the difference in symptoms or side effects.

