2.5 Patient Selection

An estimated 75 subjects with MDD in partial or full remission who are currently taking bupropion 300mg XL (branded or generic) will be enrolled. The target enrollment is 60 evaluable subjects. A 25% drop-out rate is conservatively assumed. Subjects must be on stable therapy (minimum of 4 months on bupropion 300mg XL). Subjects will be recruited from the Washington University patient population, by referrals from community physicians, and by public advertisements. Potential subjects will also be contacted by the pharmacy benefit manager Express Scripts, given a brief description of the study, and invited to contact the investigators for further information and potential recruitment/enrollment. The study will be posted on clinicaltrials.gov, once reviewed and approved by the Research Involving Human Subjects Committee (RIHSC), the FDA's Institutional Review Boards (IRB). Subjects will be screened with the Structured Clinical Interview for DSM Axis I Disorders (SCID) to determine eligibility. SCID assesses current and lifetime depression, as well as other psychiatric disorders, and is used to clarify psychiatric inclusion and exclusion criteria. Participants must have MDD which is in partial or full remission. All risks and benefits will be explained, and subjects will sign an informed consent form. After enrollment a blood sample will be obtained, coded for deidentification (see 3.3.4 below) and stored at -80°C in the PIs lab for later DNA analysis. DNA is stored until all reports and manuscripts are completed and accepted.

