2.6.2 Randomization

The order of the four study drugs will be randomized and balanced across the study. The randomization table will be generated by the Barnes-Jewish Hospital Investigational Pharmacy. Each subject will be assigned the next available number. Subjects, investigators, and all study team members will be blinded to drug treatment. In the case of dropouts (either subject- or investigator-initiated), subjects will be replaced, to provide the required number of subjects. Randomization of replacements will be as follows:

- 1. Subjects withdrawn prior to randomization (before or during the lead-in) will simply be replaced in that former subject's randomization, and receive that subject's order of drug products
- 2. Subjects withdrawn after randomization, while receiving the study drugs, will be replaced using the next scheduled randomization sequence.

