2.6.5 Randomized Study Period

Subjects will take each 300mg bupropion XL product for 6 weeks, and then be switched to another product without washout, according to their randomization schedule. During the 2nd-3rd week on each product, subjects will visit the study clinic for a bupropion pharmacokinetic session, an objective assessment of depression and side effects, and to receive another 3 week supply of study drug. During the 6th week on each product, subjects will again visit the study clinic for objective assessments of depression and side effects. Subjects will then be switched to their next scheduled drug product, and the sequence repeated for the four study drugs. Each subject will therefore be studied for four 6-week study drug epochs. Subjects will not be informed when they are being switched, in order to minimize bias. A Medication Event Monitoring System, (MEMS 6 TrackCap, or equivalent) will be used to assess compliance and compile drug dosing histories for the quantitative analysis of adherence during each subject's 28 week study period.

The rationale for the timing of the pharmacokinetic assessments is as follows: Subjects must be at steady-state on their new bupropion product. Steady-state bupropion concentrations have been reported to occur by 8d for all formulations. ¹⁸ Nevertheless, to ensure that metabolites disposition is also at steady-state, and metabolite elimination is known to be somewhat slower than parent, at least 10d will be allowed before assessing pharmacokinetics. Assessment should not wait too long, however, in case a patient reports loss of effectiveness or side effects after starting a new bupropion product, causing a product switch or other intervention, and this risk increases with time. Therefore the 10-20 day window will be targeted for the bupropion pharmacokinetic session for each product.

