2.7.4 Sample Size Justification

Calculations for sample size and power of the proposed studies are based on information from the confidence intervals for the ratio of the pharmacokinetic parameters for the generic (Budeprion XL) to the innovator (Wellbutrin XL) which was recently reported by the FDA in their evaluation of Budeprion XL.⁵¹

SAS 9.3's Proc Power was used to conduct the correct power analysis for the two one-sided tests (TOST) approach per the FDA guidance on bioequivalence. Using a 90% confidence interval and ratios needing to be between 0.80 and 1.25, the power for sample sizes ranging from a conservative estimate of 60 to the recruitment goal of 75 was computed. If the comparators are indeed bioequivalent (ratio=1.0) then the study power would be >0.999 for a pharmacokinetic parameter such as AUC and 0.98 for a more variable parameter such as C_{max} . If the generic is 10% under (or over), e.g. ratio=0.90,

then for AUC the power would be 0.78=0.83 to declare a significant difference between the compounds at an alpha of .05 even if the CI for the ration was still contained within the 0.80-1.25 bounds.

Ver 1.02

The study is also powered in order to have a reasonable power of detecting clinical differences between compounds. If one of the generics is non-equivalent with respect to symptom and it is assumed that 25% suffer a relapse on this generic versus 5% for Wellbutrin or other (equivalent) forms, then using a McNemar's test for equality of proportions, a sample size of 60 and a 1-tailed alpha of 0.05, the power will be about 0.83. For continuous variables, there will be 0.80 power to detect a standardized difference of 0.37 (low-medium effect size).

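### Daily phone scores are compared over phases that begin without washout, with no allowance for the days before steady state and no requirement that sequences balance carry-over

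*Combined protocol and SAP*

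**What the plan says.** Section 2.6.5: after 6 weeks on a product, subjects will "then be switched to another product without washout, according to their randomization schedule". Section 2.6.4 likewise has no washout between the lead-in product and the first study drug.

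Section 2.6.5 puts bupropion steady state at 8 days. Because metabolites are slower, "at least 10d will be allowed before assessing pharmacokinetics", and the PK session is targeted at days 10-20. This delay is stated for the PK session only.

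Section 2.7.3.2: daily depressive-symptom, side-effect and release-sensation scores "during each randomized bupropion phase will be compared with each other" and with the lead-in. No window is named, so the plain reading is the whole phase. The models are analogues of the PK models. Differences in scores are also to be correlated, subject by subject, with PK ratios.

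Section 2.6.2: "The order of the four study drugs will be randomized and balanced across the study". Sections 2.6.3 and 4.1.4 repeat the requirement of balance. No section names a Williams design or balance for carry-over. Section 2.7.3.1 leaves order effects out of the main model and says that they will be determined as well. No carry-over or time-since-switch term appears in the plan.

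**The concern.** The plan recognises that the first days after a switch do not represent the new product alone, and it times the PK session accordingly. The phone scores get no such allowance. Days 1-8 are 8/42 = 19% of a phase and days 1-10 are 10/42 = 24%.

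Objective 2 in section 2.3 is the patient-reported comparison of products. Section 2.6.5.3 adds the phone scores because standard measures may miss subtle effects of non-equivalent products. Dilution in that instrument favours a finding of no difference. The correlation with PK would also set scores that include the transition against PK measured after it.

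The sequence rule adds a second problem. In a cyclic Latin square each product has the same predecessor whenever it follows another study drug, so part of a deviant product's effect would be credited to the product behind it.

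**Working it through.** **Inputs.** "The target enrollment is 60 evaluable subjects" (section 2.5). Phase length is 42 days (section 2.6.3). Times to steady state are 8 and 10 days (section 2.6.5). Section 2.7.4 gives 0.80 power at a standardized difference of 0.37 for continuous variables. The assumed 25% drop-out is covered by enrolling 75 and is not applied again.

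**Reproducing the plan's figure.** Section 2.7.4 states a one-tailed alpha only for the McNemar calculation. A paired t test (noncentral t, n = 60, two-sided 5%) gives power 0.805 at 0.37 and a detectable difference of 0.368. One-sided, the detectable difference would be 0.325. Two-sided 5% therefore matches and is assumed below.

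**Model.** Let L be the share of a phase-mean score that belongs to the previous product. Let one product differ from three equivalent ones by an effect t. Period 1 follows the subject's own product.

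- *Williams design.* Each product follows each other product in one of its four periods. The deviant product averages (1 - L)t and every other product averages Lt/4. The contrast kept is 1 - L - L/4 = 1 - 1.25L.
- *Cyclic Latin square.* Each product follows one fixed predecessor in three of its four periods. The follower of the deviant product picks up 0.75Lt, and the other two pick up nothing. The contrast between deviant and follower keeps 1 - 1.75L. The follower also differs spuriously from the two equivalent products by 0.75L of the true effect.

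Least-squares fits with sequence, period and product terms give the same factors.

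**Assumed transitions.** The documents give no time course, so three shapes are shown, each ending at day 8 or day 10. First-order means five half-lives by that day. The step keeps the old product's full effect until that day and is an upper bound unless mood lags drug level.

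| Transition (day 8 / day 10) | L | Shrinkage 1.25L | Power at 0.37(1 - 1.25L) | Cyclic: spurious 0.75L | Cyclic: power, deviant v follower |
|---|---|---|---|---|---|
| First-order | 0.055 / 0.068 | 7% / 9% | 0.75 / 0.73 | 4% / 5% | 0.72 / 0.70 |
| Linear | 0.095 / 0.119 | 12% / 15% | 0.70 / 0.67 | 7% / 9% | 0.65 / 0.61 |
| Step (upper bound) | 0.190 / 0.238 | 24% / 30% | 0.57 / 0.51 | 14% / 18% | 0.47 / 0.38 |

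For example, linear over 8 days gives L = 4/42 = 0.095, a factor of 1 - 1.25 x 0.095 = 0.881, an effect of 0.37 x 0.881 = 0.326, and power 0.70.

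**Separating carry-over from product.** With a first-order carry-over term added, all product contrasts remain estimable in both designs. The variance of a product contrast, per 4 x 4 square in units of the error variance, is 0.55 for Williams and 2.75 for cyclic, a ratio of 5.

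**Cost of dropping days 1-10.** If daily scores are independent within a phase, the standard error rises by sqrt(42/32) = 1.146, about 15%. Power at 0.37/1.146 = 0.323 is then 0.69. If daily scores share a phase-level correlation of 0.3, the ratio is sqrt[((1 + 31 x 0.3)/32) / ((1 + 41 x 0.3)/42)] = 1.008, and power stays at about 0.80.

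**The case against.** **Scope.** A reader might infer that all clinical outcomes lack protection. The documents do not support that. MADRS and ASEC are collected at the week 2-3 visit, alongside the PK session, and again in week 6 (sections 2.6.5 and 2.6.5.2). Those visits fall largely after the transition, and relapse assessment is triggered by MADRS. The point is confined to the phone scores.

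**Size.** A reader might take power near 0.51 as the expected loss. That needs the old product to act in full to day 10 while the new one, taken from day 1, does nothing. First-order change, the ordinary pharmacokinetic assumption, costs 7-9%. Section 2.7.4 also does not tie its 0.37 to phone means, so the power figures are conditional on applying it there.

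**Sequences.** The randomization table is held by the pharmacy and is not in the documents. It may already balance carry-over; equal use of all 24 orders, for instance, would do so. Nothing shows that a cyclic square is used, only that the wording permits one. Nor would carry-over be inseparable from product in such a square: period 1 follows the subject's own product, so it is estimable, though inefficiently. The plan to determine order effects is a partial safeguard, but order is not carry-over.

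**Remedy.** A later window can cost as much power as it restores when noise is purely day to day: 0.69, against 0.73-0.75 for first-order dilution left alone. Section 2.6.5.3 also says that phone scoring is meant to catch transient events, and section 3.1 expects side effects early in treatment. For side-effect and release items the first days may carry the most signal. This stands, and it is why the fix treats the item types differently.

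**Conclusion.** The concern holds for the daily phone scores. They are compared over whole phases that begin with a mixture of two products, and the sequence rule does not exclude a design that handles carry-over poorly.

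Under carry-over-balanced sequences, product contrasts shrink by about 7-9% (first-order), 12-15% (linear) or at most 24-30% (full effect for 8-10 days). The corresponding power is about 0.73-0.75, 0.67-0.70 or 0.51-0.57, if the 0.37 SD figure is applied to whole-phase phone means with n = 60 and two-sided 5%. A cyclic square would add a spurious difference of about 4-18% of the true effect for the product behind a deviant one.

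The transition shape is an assumption throughout. The dilution applies to effects that track steady-state exposure, not to sensations confined to the first days. The loss is modest under gradual change but acts towards finding no difference, so it is worth correcting. It does not call the PK endpoints or the no-washout design into question.

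**What to change.** 1. Section 2.6.2: require sequences from a Williams design, so that each product follows every other equally often. This costs nothing. Four sequences suffice, and 60 evaluable subjects make 60/4 = 15 per sequence. It prevents the spurious difference between equivalent products but does not remove the dilution.
2. Section 2.7.3.2: prespecify days 11-42 of each phase as the window for phone depressive-symptom comparisons and for the correlation with PK. Keep the whole phase as a sensitivity analysis.
3. Section 2.7.3.2: for side-effect and release-sensation items, keep the whole phase as the main comparison and report days 1-10 and days 11-42 separately, because these effects may be early or transient.

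Items 2 and 3 take a few sentences and change no visit or treatment. The price of the window is a standard error up to about 15% larger if all noise is day to day, and under 1% larger if daily scores share a phase-level correlation of 0.3 or more. At the high end the gain is less bias, not more power.

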2.1.5 CYP2B6, Genetics and Bupropion Metabolism and Disposition

There is extensive interindividual variability in CYP2B6 activity, due to variability in protein expression, susceptibility to inhibitors (clopidogrel, ticlopidine, thiotepa) and inducers (rifampin, phenobarbital, phenytoin),³⁴⁻³⁶ and *CYP2B6* genetic polymorphisms.^{36,37} Moreover, CYP2B6 is highly polymorphic, with 37 haplotypes (star alleles) identified to date, several of which have major clinical importance.^{36,37} Bupropion hydroxylation is diminished, both in expressed CYP2B6.6 compared with wild-type CYP2B6.1,^{38,39} and in human liver microsomes from CYP2B6*6 carriers.^{39,40} After 7 days of sustained-release bupropion dosing, CYP2B6*6 and *18 carriers had significantly reduced plasma hydroxybupropion concentrations, with no effects on bupropion.^{41,42}

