2.5.1 Inclusion Criteria

Each subject must meet all of the following criteria:

- 1. Adult outpatients age 18-75 years
- 2. Currently on once daily bupropion HCl 300mg XL (brand or any generic), for a minimum of 4 months

- 3. Major depressive disorder (MDD), in partial or full remission for at least 4 months, as confirmed by the SCID. Spontaneous relapse of depression unrelated to medication changes is less likely about 5% chance per year after remission has been maintained for at least 4 months.²
- 4. Ability to understand and willingness to comply with study procedures, and to provide written informed consent

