The rationale for not informing subjects of the timing and frequency of product switching is to minimize expectancy. Patients are more likely to report an increase in depressive symptoms or side effects if they identify a change in medication. In previous relapse prevention studies, patient complaints about lack of efficacy increased, regardless of treatment (continued medication or taper to placebo), when their medication changed from pills to over-encapsulated. In another, patients reported increased symptoms at the time of randomization, apparently from anticipation. Expectancy effects are particularly common in depression studies, and interfere with detection of product switch-related clinical effects. Therefore: (1) participants will not be told when or how many times they are being crossed over; (2) all bupropion products will be over-encapsulated to look identical throughout the study, including during the lead-in phase.

Particular attention will be paid to maximizing medication adherence. To maximize adherence:

- Patients will be carefully screened, to screen out those with low likelihood of good medication adherence. Potential participants with known predictors of poor adherence (e.g. heavy drinking, dissatisfaction with their bupropion therapy, adverse side effects, perceived lack of benefit from bupropion) will not be enrolled.
- Adherence and timing of medication will be evaluated during the lead-in phase; subjects showing non-adherence during the lead-in phase will be removed.
- Subjects will receive daily reminders to take their pill, and reminders regarding the importance of exact adherence.
- Adherence and timing of medication will be confirmed with the MEMS system (cap with a microprocessor, providing real-time data on container opening), in addition to self-reports and pill counts.
- Patients showing non-adherence in the 7 days before bioequivalence testing will be rescheduled. At other times, adherence will be corrected and reinforced using reminders, engaging participants and their support systems, and reassessing barriers and facilitators to adherence.

After the fourth 6-week drug session and at the last study clinic visit, subjects will be returned to their original bupropion product, resupplied with their own medication to take, and thanked and provided positive feedback for their participation.

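### The exploratory PK-symptom covariate model in 2.7.3.2 does not separate within-patient from between-patient exposure, so its coefficient may not answer the product question

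*Combined protocol and SAP*

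**What the plan says.** Section 2.7.3.2 sets the base model for the daily phone scores: "Repeated measures ANOVA analogues of the models described above for the pharmacokinetic parameters will be used". Those models are in 2.7.3.1, which describes a repeated measures model per parameter, expects most PK parameters to be log-transformed, and does not say whether patient is fixed or random.

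The section then plans two exploratory analyses that link PK to patient reports:

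- The first asks whether differences in the phone reports "are related to pharmacokinetics by augmenting the models above with pharmacokinetic parameters as covariates". Neither centring on the patient's own mean nor the scale of the covariate is mentioned.
- The second works by "correlating, on an individual basis, the ratio of the two pharmacokinetic parameters to the difference in symptoms or side effects".

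Under 2.6.1 and 2.6.3, each patient takes all four products and has one PK session on each, so there are four values of each PK parameter per patient. Section 2.1.5 states: "There is extensive interindividual variability in CYP2B6 activity, due to variability in protein expression". Section 2.2 reports that the CYP2B6*6 allele changed hydroxybupropion concentrations with a gene-dose effect. Sections 2.1.5 and 2.2 both report no genotype effect on bupropion itself.

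**The concern.** The question is within-patient: when a product gives a patient a different exposure, does that patient report different symptoms? A PK value that is not split by patient carries two kinds of variation. One is the difference between products in the same patient. The other is the stable difference between high-exposure and low-exposure patients. A model with a random patient effect, or a compound-symmetric covariance, uses both and returns one coefficient for the two slopes.

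The between-patient slope is not protected by randomisation. It can reflect genotype, age or weight. Enrolment may also shape it, because every patient must have "Major depressive disorder (MDD), in partial or full remission for at least 4 months, as confirmed by the SCID", and 2.6.5 screens out people with "dissatisfaction with their bupropion therapy, adverse side effects, perceived lack of benefit from bupropion". There is therefore no reason to expect the two slopes to agree.

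Two errors are possible, in different circumstances. If only a between-patient association exists, it may be reported as symptoms tracking product pharmacokinetics. If a real within-patient link exists and the between-patient slope is flat or opposite, the link may be missed.

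**Working it through.** **1. The plan's nearest figure.** No power is stated for the PK-symptom slope. For continuous outcomes, 2.7.4 gives 0.80 power at a standardised difference of 0.37. A paired t-test with n = 60 and two-sided alpha 0.05 gives 0.805, so that figure reproduces.

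**2. Within-patient SD of log AUC.** Section 2.7.4 gives power of 0.78 to 0.83 for an AUC ratio of 0.90 and sample sizes of 60 to 75. Taking 0.78 as the value at n = 60, two-sided 0.05:

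- Paired SD ≈ |ln 0.90| × √60 / (2.001 + 0.772) = 0.1054 × 7.746 / 2.773 = 0.294.
- Within-patient SD = 0.294 / √2 = 0.208.

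Taking 0.83 as the value at n = 75 gives 0.1054 × 8.660 / (1.993 + 0.954) = 0.310, or 0.219 within patient, which is similar. This input comes from the FDA comparison of another generic, described in 2.1.3 as single-dose in healthy subjects. It is only a rough anchor for steady state in patients, and 2.7.4 does not name the analyte.

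**3. Weight on the between-patient slope.** Take K = 4 products, score variance scaled to 1, ICC ρ, between-patient SD of log PK s_B and within-patient SD s_W. The information per patient is:

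- Within: W = (K − 1) s_W² / (1 − ρ)
- Between: B = K (s_B² + s_W²/K) / (1 − ρ + Kρ)
- Weight on the slope across patient means = B / (W + B)

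The values of s_B and ρ are assumed; the documents give neither. With s_W = 0.208 (s_W² = 0.0433):

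| Case | s_B | ρ | W | B | Weight |
|---|---|---|---|---|---|
| Low | 0.30 | 0.85 | 0.865 | 4 × 0.1008 / 3.55 = 0.114 | 0.12 |
| Middle | 0.45 | 0.70 | 0.433 | 4 × 0.2133 / 3.10 = 0.275 | 0.39 |
| High | 0.60 | 0.50 | 0.260 | 4 × 0.3708 / 2.50 = 0.593 | 0.70 |

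**4. False rejection when there is no within-patient link.** Two simulations used 60 patients, four products and product effects in the model.

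- *First* (s_B 0.3-0.6, ρ 0.5-0.85): a between-patient correlation of 0.3 gives 29% in the middle case (range 12-43%). A correlation of 0.4 gives 49% (range 19-68%). The split covariate stays at about 5%.
- *Second* (between-patient CV 0.40-0.50, within-patient CV 0.15-0.30, ρ 0.30-0.85, correlation 0.40): the unsplit random-intercept slope rejects in 21-70% of runs and the within-patient slope in 4.0-6.4%. With CVs of 0.50 and 0.20, ρ = 0.70, a true between slope of 0.78 and a within slope of 0, the mean fitted slope is 0.31, which is the blend itself.
- With no link at either level, the unsplit slope rejects in 4.6-6.8%. The fault therefore needs the two slopes to differ.

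**5. Power when the within-patient link is real** (second simulation, ρ 0.5-0.7, within-patient correlation about 0.24).

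| Analysis | Power |
|---|---|
| Within-patient slope, all four products | 0.90-0.92 |
| Unsplit slope, no between-patient link | 0.61-0.84 |
| Unsplit slope, opposite between-patient link | 0.10-0.39 |
| Planned ratio-versus-difference correlation, one product pair | 0.41-0.51 |

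The first simulation, in its middle case with a zero between-patient slope, gives 59% for the unsplit slope against 78% for the split one.

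**6. The plan's second analysis.** The ratio-versus-difference correlation rejects in 3.4-6.4% of runs when only a between-patient link exists. Differencing removes stable patient-level effects.

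**The case against.** The strongest reply is that the plan already contains a clean within-patient analysis in the very next sentence. That is correct. A reader might infer that the unsplit covariate is the only test of the PK-symptom link, or that the plan gives up the advantage of patients acting as their own controls. The text supports neither inference. What remains is that the correlation compares two products at a time and has roughly half the power of a pooled within-patient slope, and that the plan does not say which result governs if the two disagree.

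Second, blending requires that patient is not a fixed effect, and the plan does not say so. With fixed patient effects the same covariate yields the within-patient slope. The interest in 2.7.3.1 in interpatient variability and in genotype as a predictor leans towards random effects but does not settle it. This limits the point to a conditional one.

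Third, a reader might take the CYP2B6 text as evidence of distortion for parent bupropion. Sections 2.1.5 and 2.2 say the opposite for the parent, so the documented mechanism applies to hydroxybupropion. No within-patient SD for that metabolite can be derived from the plan. Co-medication acting through CYP2B6 is also limited by exclusion criterion 6 in 2.5.2.

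Fourth, false rejection and dilution are alternative scenarios, not harms to be added together. Finally, log transformation is anticipated for the PK models. It does not separate the two slopes, but it would be wrong to say that the plan commits to untransformed values.

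**Conclusion.** The point holds in a conditional and minor form. As written, the covariate analysis does not identify the within-patient slope. If it is fitted with random patient effects or compound symmetry, and the between- and within-patient slopes differ, its coefficient can mislead in either direction. Under the assumed values, false rejection is roughly 12-70% for a between-patient correlation of 0.3-0.4, against about 5% for the split covariate.

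Those figures rest on assumed between-patient spread, ICC and correlation, and on a within-patient SD borrowed from another setting. They show what could happen; they do not estimate this trial's error rate. The effect is small if scores are very stable within patients and exposure varies little between them, and it vanishes with fixed patient effects. A reader might also infer that the bioequivalence, relapse or product-comparison results are affected. They are not: the analysis is exploratory, and no PK-symptom relation is among the endpoints in 2.7.1.

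**What to change.** In 2.7.3.2, state how patient enters the model. Then do one of the following:

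- Replace each (log) PK covariate by two terms: the patient's mean over the periods observed, and the product-specific deviation from that mean.
- Fit patients as fixed effects in this analysis.

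Base any statement that product differences in symptoms, side effects or release reports are related to pharmacokinetics on the within-patient coefficient, read alongside the planned ratio-versus-difference correlation. If the split is used, report the patient-mean coefficient as descriptive only.

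The cost is one or two sentences and, for the split, one derived variable per PK parameter; no new data are needed. The downside is some loss of precision if the two slopes are truly equal, because between-patient information is no longer pooled.

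### Section 2.7.3.2 says product differences in phone scores will be determined by correlating PK ratios with symptom differences, but a correlation answers an exposure-response question, not whether products differ

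*Combined protocol and SAP*

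**What the plan says.** Section 2.7.3.2 describes two routes from the phone data to a statement about products.

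- **Direct comparison (second paragraph).** "Repeated measures ANOVA analogues of the models described above for the pharmacokinetic parameters will be used", and "any systematic effects of differences between patient's responses to Wellbutrin XL and each generic product will be tested". This is a mean brand-versus-generic comparison within patients.
- **Link to pharmacokinetics (last paragraph).** It opens as exploration: "Analysis will explore whether differences in smart phone-collected depression symptoms, side effects, and patient reports regarding release patterns are related to pharmacokinetics". The tool for this is the direct-comparison model with PK terms added to it. The next sentence makes a firmer claim: "Analysis will determine if there are differences in bupropion products by correlating, on an individual basis, the ratio of the two pharmacokinetic parameters" with the difference in symptoms or side effects.

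The correlation step has no intercept, mean contrast, decision rule, alpha or power. The section does not say which route governs if the two disagree. It also does not say which two PK parameters form the ratio: the natural reading is one parameter on generic over the same parameter on brand, but two different parameters would also fit the words.

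**The concern.** A product effect is a shift in a mean: the average generic/brand exposure ratio moves away from 1, or the average symptom difference moves away from 0. A correlation subtracts both averages before it does anything else. What remains is whether patients whose own ratio is above average also have an above-average symptom difference. That is a question about exposure and response.

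Comparing self-reported differences between products is Objective 2 (section 2.3). Someone applying the sentence literally could report a significant correlation as a product difference, or a null correlation as evidence that the products feel the same. Neither follows.

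The PK-augmented model needs similar care. Exposure lies downstream of the product, so a product term adjusted for PK is no longer the whole product difference. A single PK covariate also mixes differences between patients with changes within a patient. The protocol itself describes a between-patient source: CYP2B6*6 alters hydroxybupropion concentrations, though not those of bupropion (sections 2.1.5 and 2.2).

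**Working it through.** **Inputs**

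- Patients: n = 60 ("The target enrollment is 60 evaluable subjects", section 2.5).
- Benchmark for a continuous score: "there will be 0.80 power to detect a standardized difference of 0.37" (section 2.7.4). Neither alpha nor sidedness is given for this sentence; two-sided 0.05 is assumed.
- SD of the log AUC ratio: not stated. Section 2.7.4 says "for AUC the power would be 0.78=0.83 to declare a significant difference between the compounds at an alpha of .05" at a ratio of 0.90. Solving the paired test for power 0.78 at n = 60 gives an SD of about 0.294. It only sets the scale of the simulations; the correlation results do not depend on it.
- Correlation between the log PK ratio and the symptom difference: not stated. Values of 0.3 to 0.5 are assumed below.

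**Step 1. Reproduce the plan's figure.** For a paired t test the noncentrality is d√n = 0.37 × √60 = 2.866. With 59 degrees of freedom and a critical value of 2.001, power is 0.805, matching the stated 0.80. That power belongs to the mean contrast.

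**Step 2. What the correlation can see.** For patient i, let x_i be the log generic/brand PK ratio and y_i the generic-minus-brand symptom difference. Then

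r = Σ(x_i − x̄)(y_i − ȳ) / √[Σ(x_i − x̄)² Σ(y_i − ȳ)²].

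Replace x_i by x_i + a and y_i by y_i + b. The means move by a and b, every deviation is unchanged, and so is r. On the raw scale a common proportional change multiplies every ratio by one constant, and r is again unchanged. A product effect shared by all patients is exactly such an a or b.

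**Step 3. Real mean difference, no patient-level link.** At n = 60 the correlation is significant when |r| exceeds 2.0017 / √(58 + 2.0017²) = 0.254. Simulated rejection rates, with AUC 20% low on the generic:

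| Common symptom shift | Correlation | Paired mean contrast |
|---|---|---|
| 0.37 SD | about 5% | 81% |
| 1.0 SD | about 5% | about 100% |

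The 5% follows from step 2; the simulation only confirms it.

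**Step 4. Identical product means, symptoms tracking the ratio.** By the Fisher approximation, power = Φ(√57 · atanh(ρ) − 1.96), ignoring the negligible opposite tail.

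- ρ = 0.3: 7.550 × 0.3095 = 2.337, so Φ(0.377) = 0.65.
- ρ = 0.4: 7.550 × 0.4236 = 3.198, so Φ(1.238) = 0.89.
- ρ = 0.5: 7.550 × 0.5493 = 4.147, so Φ(2.187) = 0.99.

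Simulations gave 65 to 66%, 89 to 90% and 99%. The mean contrast rejected in about 5% throughout, as it should when means are equal.

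**Step 5. Pooling the three generic-brand pairs.** The plan does not exclude this. If one generic is 25% low with a 0.8 SD shift and the others match brand, the pooled correlation is significant in 52% of trials. For one generic 10% low with a 0.37 SD shift it is 12%. A shift shared by all three generics still drops out (11%). With no effect at all the rate is about 10%, because the pairs share the brand measurement and the simple test ignores that.

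**The case against.** The strongest reply is that nothing depends on this sentence. The paragraph before it already plans the mean comparison of Wellbutrin XL with each generic, and section 2.7.3.3 plans the same for MADRS and the side-effect checklist. The paragraph opens as exploration, and the correlation is to be done patient by patient, which is how one would describe an exposure-response analysis. On this view only a loose verb is at fault. The first part stands: the trial would not miss a mean difference because of this step. The second stands only in part, because the sentence names product differences as its target and says they will be determined.

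Three stronger readings are tempting, and the documents do not support them.

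- **That the conclusion on patient-perceived differences rests on the correlation.** It does not; the direct tests are in the same section.
- **That day-to-day PK noise by itself produces false signals.** Noise unrelated to symptoms weakens a correlation. The rates in step 4 need symptoms to track the measured ratio, and no document gives the strength of that link. PK comes from one session per product (section 2.6.5) while phone scores cover the whole phase, so the link may be weak. The narrower point holds: with one session per product, a significant correlation cannot separate a lasting patient-by-product effect from occasion-to-occasion variation.
- **That the plan will read the PK-adjusted product term as the product difference.** It nowhere says so. The advice on that model is a safeguard.

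It is also fair to say that section 2.7.3.1 already expects log transformation of most PK parameters, so the log scale suggested here is in keeping with the plan.

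**Conclusion.** The sentence is wrong as written, with limited consequence. Analysed pair by pair, the correlation has no power beyond its 5% error rate for a common product shift of any size. It can be significant with identical product means in about 65% to 99% of trials if symptom differences correlate with the log ratio at 0.3 to 0.5. The first result is algebraic and needs no assumption about SDs, only that pairs are analysed separately and the shift is common to patients. The second rests on assumed correlations. If pairs are pooled, the statistic carries some product information, but its nominal error rate no longer holds.

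A significant result should therefore not be reported as a product difference, nor a null result as reassurance. The primary Cmax and AUC analyses are untouched, and the planned mean contrasts remain a valid route to Objective 2. What needs correcting is a stated inference rule that would answer that objective wrongly if followed.

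**What to change.** Amend section 2.7.3.2 as follows.

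1. State that product differences in phone scores are concluded only from the mean within-patient generic-minus-brand contrasts already planned.
2. Relabel the individual-level step as exploratory exposure-response. Regress the symptom or side-effect difference on the log generic/brand ratio of a named PK parameter, separately for each generic-brand pair or with a model that allows for the shared brand measurement.
3. In the PK-augmented model, enter log PK as the patient's mean plus the deviation from that mean. The within-patient slope is then not mixed with differences between patients, such as CYP2B6 effects on hydroxybupropion.
4. State that the PK-adjusted product term is not to be read as the product difference.

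The cost is SAP wording and slightly more analysis work. No new data are needed.
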